Protocol

ECHO study

The Effect of Copper on the Healing of Obstetric wounds

VERSION 3 – 17/09/2015

Authors:

[name] MD, Research Fellow in Urogynaecology

[name] MD, FRCOG, Consultant Obstetrician & Gynaecologist, Urogynaecology subspecialist

[name] MD, FRCOG, Consultant Obstetrician & Gynaecologist

Croydon University Hospital

[name]

Croydon, United Kingdom

[contact]

Full title: Randomised controlled trial on the effect of copper impregnated dressings and maternity pads on the healing of obstetric wounds and wound infection

[figure not shown]
Background

In Croydon Health Services around 4,000 babies are born annually and the vast majority are born vaginally. The most common complication of vaginal delivery is perineal or vaginal laceration with a prevalence as high as 85% and up to 70% will need suturing (1). Within Croydon Health Services 73% deliver vaginally of whom 66% sustain perineal laceration (19% first degree, 74% second degree, 7% 3rd/4th degree) and an episiotomy is performed in 24% of the vaginal deliveries. Minor lacerations are often left unsutured, whereas the majority of the second or higher degree tears will be sutured directly after delivery. Due to supporting factors such as a moist environment and the presence of high numbers of bacteria, perineal trauma is associated with wound infection and affects 11% of the women with sutured tears (2). Wound infection can cause pain, dehiscence, delayed wound healing and interfere with a woman's ability to nurture their baby and enjoy motherhood (3).

The caesarean section rate worldwide is rising (4) and the rate in Croydon University Hospital is in the region of 25% of all deliveries. The most significant source of maternal morbidity after caesarean section is postoperative infection (surgical site infection) and can be the cause of a prolonged hospital stay, readmissions (5) sepsis and maternal death (6). Surgical site infection is one of the most prevalent reported nosocomial infection, which accounts for 14-16% of all hospital-acquired infections. Despite prophylactic antibiotics, the rate of wound infection after caesarean section is ranging between 7% and 41% (7-9).

According to the Centers for Disease Control and Prevention (CDC), surgical site infection can be classified as an incisional infection, either superficial or deep, or an organ or space infection, such as endometritis (10). See figure one for the CDC surgical site classification.

Figure 1 CDC Classification for Surgical Site Infections

The micro-organisms that are most commonly the cause of the infection of perineal tears and caesarean section wounds are Enterococci, Streptococci, Staphylococci, Gram-negative bacteria and anaerobes (5, 11). As a consequence of antibiotic resistance, MRSA infection is becoming an increasing challenge. Several studies have detected MRSA colonisation rates of up to 10% in rectovaginal swabs in asymptomatic pregnant women (12, 13). MRSA has been proven to cause more severe postpartum infections, especially after caesarean section (14-16). Although several strategies to eliminate or reduce colonisation of MRSA such as skin wash have been studied, the real efficacy of such interventions remains inconclusive (17). Moreover, the preoperative skin preparation using chlorhexidine, which reduced the overall rate of surgical site infection, was found ineffective among MRSA carriers (18).

Antimicrobial copper

The antimicrobial effect of copper has been known for centuries. As early as 2600-2200 BC the Egyptians used green copper rust for the treatment of chest wounds and to sterilise drinking water. In another Papyrus it was written that copper splinters, shavings and various

copper salts and oxides were used to treat headaches, burn wounds, itching and skin infections (19). With the increase in antibiotic resistant bacteria causing nosocomial infections, copper has become a popular subject of recent research. There are many laboratory studies showing the biocidal effect of copper on a wide range of microbes such as bacteria, fungi and viruses (20, 21). Copper has also been proven to be effective against Methicillin-resistant *Staphylococcus aureus* (MRSA) (22) and Vancomycin-resistant Enterococci (VRE) (23). The use of copper surfaces within the hospital setting has been evaluated in several clinical studies showing significant reductions in bacterial colonisation on copper surfaces compared to standard materials (24). After the use of copper as a biocidal contact surface, the use of copper impregnated textiles was explored. Although there is a variety of containing copper impregnated textiles available such as socks, pyjamas, underwear, bed linen, face masks, stockings and wound dressings, there is a paucity of clinical research. There has however been a clinical study on the effect of copper impregnated socks in patients suffering from tinea pedis and this revealed a significant improvement or resolution of the infection after wearing these socks for two weeks (25).

Wound healing

Copper is assumed to be involved in several processes crucial for wound healing (26). A key role in wound healing is angiogenesis. It has been shown that copper induces the production of vascular endothelial growth factor (VEGF) and therefore stimulates angiogenesis (27). Furthermore, copper promotes wound healing due to an elevation in integrin expression (28); enhancement of fibrinogen stabilisation (29) and up regulation of several enzymes essential for matrix remodelling and cell growth (30). Several laboratory studies have demonstrated an association between a copper dependant enzyme, lysyl oxidase (LOX), and skin ageing and pathological skin conditions (31).

Safety

The dermal exposure to copper is considered safe as copper is not only an essential element for normal skin function but also essential for the immune system and blood coagulation (32). In contrast to microorganisms, human skin cells have the ability to metabolise and utilise copper (33) and therefore the development of adverse reactions are unlikely.

Our hypothesis is that copper impregnated fibres in maternity pads and surgical wound dressings, reduces infection rates in perineal lacerations, episiotomies and caesarean section wounds.

Aim

The aim of this study is to investigate the impact of copper impregnated wound dressings and maternity pads on the incidence of infection in perineal wounds after vaginal delivery and caesarean section wounds.

Objectives

Primary:

1. To assess the effect of copper impregnated wound dressings on the incidence of wound infection following caesarean section.
2. To assess the effect of copper impregnated maternity pads on the incidence of wound infection of second degree perineal tears following vaginal delivery.

Secondary:

1. To assess the effect of copper impregnated wound dressings on other maternal outcomes, such as length of hospitalisation, readmission rate and pain of the wound.
2. To assess the effect of copper impregnated maternity pads on other maternal outcomes, such as length of hospitalisation, readmission rate and perineal pain.

Methodology

This is a double blind randomised controlled pilot study to assess feasibility of copper impregnated wound dressings and maternity pads for the healing of obstetric wounds. All pregnant women in Croydon University Hospital who attend their routine second-trimester scan appointment at approximately 20 weeks of gestation will receive a detailed patient information sheet (Appendix 1 Patient Information Sheet) about the four arms of this study. When women are eligible to participate after delivery, informed consent will be obtained (see Appendix 2 Informed Consent).

All women who are planned to have an elective caesarean section will be recruited at their antenatal clinic appointment. A detailed patient information sheet specific for the caesarean section arm of this study will be given prior to consent. Informed consent will be obtained antenatally. After caesarean section, confirmation of willingness to participate in this study will be obtained and documented directly after elective caesarean.

All patients will be assessed by telephone at baseline, 7, 14, and 30 days. The recruitment period will be 12 months.

The inclusion criteria are:

- Aged 18 or over
- Delivered by caesarean section (emergency or elective),
or vaginally, sustaining a perineal tear or episiotomy which needed to be sutured
- Ability to understand the content of the patient information sheet (in English, via an interpreter if needed and possible)
- Ability to give informed consent

The exclusion criteria are:

- Inability to give consent
- Fetal or neonatal death or poor neonatal outcome
- Obstetric anal sphincter injuries
- Included in another study on postpartum infection conducted in the Obstetrics and Gynaecology Department
- Wilson's disease
- Allergy to copper

Randomisation

After inclusion all patients will be randomised for a wound dressing or maternity pad with (study group) or without copper (control group). The two sets of wound dressings and pads will be marked "A" or "B". Both the clinician and the patient will be blinded to the randomised group. Only the manufacturer will be aware of which group contains copper.

Copper impregnated dressings

As soon as possible, but within 12 hours after primary closure of the caesarean section incision, the randomised study dressing will be applied. The two study dressings will be equivalent to the dressing normally used within this Trust, except that one set of dressings will have a thin top layer of non-woven polyester fibres with 3% copper oxide ions permanently attached to it. According to local protocol the wound dressing will be left intact for 7 days following surgery and will be renewed if necessary.

Copper impregnated maternity pads

As soon as possible, but within 12 hours after suturing women will be asked to wear the study maternity pads, which will be provided. The two sets of study maternity pads will be equivalent to the currently recommended pads, except that one set of pads will have a thin

top layer of non-woven polyester fibres with 3% copper oxide ions permanently attached to it. Women will be asked to use the pads for 14 days after delivery.

Patient data, history and physical examination:

Demographic data such as age, ethnicity, height and weight will be collected as well as obstetric data and delivery details (Appendix 4 Datasheet). Past medical history such as concomitant (chronic) diseases and the use of medications will be obtained. Wound infection will be assessed via a telephone questionnaire after 7, 14 and 30 days after delivery.

The data will be stored in a secure room within Trust facilities. All electronic data will be stored within password protected IT system within the Trust, which is only accessible by the clinical and research team.

Questionnaire

For the assessment of surgical site infection, the Post Discharge Questionnaire (see Appendix 5 Post Discharge Questionnaire) used by the HPC surgical site infection surveillance will be used, which is according to the worldwide used definition of surgical site infection by the CDC (10). Since the Post Discharge Questionnaire is dependent on the women's report rather than confirmation following clinical assessment of the wound, the criteria for infection have modified to allow for easy interpretation of the reported symptoms as follows:

- Criterion 1: discharge pus AND antibiotics prescribed
- Criterion 2: clinical signs* AND dehiscence
- Criterion 3: Clinical signs* AND antibiotics prescribed

*clinical signs: at least 2 of the following must be present: pain, heat, redness or swelling

Without clinical assessment of the wound, the type of SSI cannot be defined.

Since there is no commonly used definition in the literature for wound infection following perineal tears, the Post discharge Questionnaire with the modified criteria for infection will be used for the perineal tears as well.

Microbiological assessment

When wound infection is suspected according to the above explained criteria, a wound swab is taken to detect the causative organisms.

Statistical analysis

Statistical analysis will be performed using SPSS version 20.0 or higher. Infection rates in the perineal tear group and the caesarean section group will be analysed. The infection rates in the study group (with copper) will be compared to the control group and possible risk factors for infection will be explored.

Sample size calculation

Since the effect of copper on infection rates is currently unknown, we will conduct a pilot study for 12 months. After 3 months we will perform an interim analysis to be able to calculate the sample size.

Maternity statistics at Croydon University Hospital	
	Past 12 months (N=3752)
Vaginal deliveries (N=2734)	
Episiotomy	643
2nd degree tear	1334
Total sutured tears (excl 3 rd /4 th degree tears)	1977
Caesarean Section (N=1018)	
EmCS	696
EICS	322
Total study population	2995

References

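### The protocol text plans no skin-reaction or adverse-event outcome for the copper products, and Criterion 3 could count a copper contact reaction as a wound infection

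*Combined protocol and SAP*

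**What the plan says.** - **Background, Safety.** Dermal exposure is held to be safe because human skin cells can metabolise copper, and "therefore the development of adverse reactions are unlikely". Earlier in the Background, on copper textiles, the protocol concedes that "there is a paucity of clinical research".
- **Exclusion criteria.** "Allergy to copper" and Wilson's disease are baseline exclusions. Nothing about reactions follows after randomisation.
- **Objectives.** The secondary objectives cover "other maternal outcomes, such as length of hospitalisation, readmission rate and pain of the wound" for dressings and "other maternal outcomes, such as length of hospitalisation, readmission rate and perineal pain" for pads.
- **Patient data, history and physical examination.** "Wound infection will be assessed via a telephone questionnaire after 7, 14 and 30 days after delivery". The text describes no other content for these calls.
- **Questionnaire.** Infection rests on the woman's own report. Criteria 1 and 2 need pus or dehiscence. The third route needs neither: "Criterion 3: Clinical signs* AND antibiotics prescribed", where "clinical signs: at least 2 of the following must be present: pain, heat, redness or swelling".
- **Microbiological assessment.** A swab is taken once infection is suspected, but its result enters none of the three criteria.
- **Statistical analysis.** Infection rates by arm and risk factors for infection are the only analyses named.

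**The concern.** Two things are at stake.

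First, the product lies against a closed surgical incision for 7 days or a sutured perineum for 14 days, and the protocol itself calls its clinical evidence base thin. Local tolerability is an obvious question for a pilot study to answer. The text provides no outcome or analysis that would answer it specifically. Excluding women with a copper allergy at entry can only remove those who already know of one.

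Second, the gap reaches the primary endpoint. A contact reaction can show as redness with swelling or heat. If antibiotics are then prescribed, Criterion 3 is met without pus, culture or clinical examination. Blinding does not prevent this, because the error would come from the product and not from the assessor. The products differ only in the copper-bearing top layer, so any reaction to that layer adds false infections to one arm. The inflated rate would also enter the 3-month interim analysis from which the sample size is to be calculated.

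**Working it through.** The protocol states no reaction rate, effect size, significance level or target number, so it has no figure to reproduce. What follows is an illustration.

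**Inputs from the documents.** Control infection rate p0: 11% for sutured perineal tears and 7% to 41% after caesarean section (Background). Annual numbers: 1,977 sutured tears and 1,018 caesareans (Sample size calculation).

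**Assumptions, not in the documents.** r is the share of uninfected copper-arm women whose reaction to the copper layer meets Criterion 3, taken as 1% to 3%. This is narrower than a reaction rate, since it also requires two listed signs and an antibiotic. True risk ratio (RR): 1 or 0.75.

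**Formula.** True copper rate c = p0 × RR. Observed copper rate = c + r(1 − c). Observed RR = observed copper rate / p0.

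**Worked example, p0 = 11%.**
- No effect, r = 1%: 0.11 + 0.01 × 0.89 = 0.1189, and 0.1189/0.11 = 1.08. With r = 3%: 0.1367/0.11 = 1.24.
- True RR 0.75: c = 0.0825. With r = 1%: 0.0825 + 0.01 × 0.9175 = 0.0917, RR 0.83. With r = 3%: 0.0825 + 0.03 × 0.9175 = 0.1100, RR 1.00.

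| Control rate | Observed RR if true RR = 1 (r = 1% to 3%) | Observed RR if true RR = 0.75 (r = 1% to 3%) |
|---|---|---|
| 11% (perineal) | 1.08 to 1.24 | 0.83 to 1.00 |
| 7% (caesarean, low end) | 1.13 to 1.40 | 0.89 to 1.16 |
| 41% (caesarean, high end) | 1.01 to 1.04 | 0.77 to 0.80 |

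**Chance of a false harm signal with no true effect.** Further assumptions: every eligible woman in a year is recruited, allocation is 1:1 (988 per arm perineal, 509 per arm caesarean) and the test is two-sided at 0.05. These arm sizes are ceilings. For the perineal case at r = 3%, the difference is 0.0267 and its standard error is √[(0.11 × 0.89 + 0.1367 × 0.8633)/988] = 0.0148, so z = 1.81 and the chance of exceeding 1.96 is about 44%. For r from 1% to 3% the chance is about 9% to 44% (perineal), 8% to 36% (caesarean at 7%) and 4% to 8% (caesarean at 41%). With no misclassification it is 2.5% in that direction.

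**Reactions to the base material.** If r = 1% applied equally in both arms at p0 = 11%, a null effect would stay at RR 1. A true RR of 0.75 would appear as 0.0917/0.1189 = 0.77. That is mild dilution, not false harm.

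**The case against.** The strongest reply is that the data forms cannot be seen. The Appendix 4 Datasheet and the Appendix 5 Post Discharge Questionnaire are cited but were not available to check, and the secondary outcomes are an open list. A reader might infer that no skin reactions are collected at all and that safety cannot be reported. The documents do not support that. A form may hold such an item. Pain and readmission are stated outcomes, and the signs needed for the infection criteria could be compared by arm, though none is specific to a skin reaction. What stands is that the protocol text specifies no collection and plans no safety outcome or analysis. An unseen form item would not supply the analysis.

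Three further replies have force:
- A reader might infer that any reaction treated with antibiotics becomes an infection. Criterion 3 also needs at least two listed signs, so an itch or rash with only one would not count.
- A reader might infer that the error can occur in one arm only. The rule is the same in both arms, and a reaction to the base pad or dressing would count in controls too. Only the excess due to the copper layer is differential.
- Excluding women with a copper allergy is compatible with calling reactions unlikely, so the protocol does not contradict itself here.

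**Conclusion.** The point holds in limited form. The protocol text plans no specific local-safety comparison for the copper products, and Criterion 3 has no means of separating a contact reaction from an infection. Any misclassification due to the copper layer would work against copper: it could hide a benefit or mimic harm, but it would not create a false benefit.

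The size is unknown. The 1% to 3% is purely an assumption, and nothing in the documents shows that copper-layer reactions occur at that level. A reader might infer that a real benefit would vanish. At an 11% control rate a true RR of 0.75 is fully masked only at the 3% end of the assumed range. At 7% it could be reversed (1.16 at 3%). At 41% the distortion is small (0.77 to 0.80). The concern therefore matters most where background infection is low. The remedy is cheap, and the data would be hard to recover afterwards, which makes the change worth making before recruitment.

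**What to change.** 1. On the existing day 7, 14 and 30 calls, ask about itching, rash or blistering under the pad or dressing, whether the woman stopped using the product because of skin symptoms, and why any antibiotic was prescribed. If the appendices already contain these items, cite them in the protocol.
2. Name local skin reaction by arm as a secondary safety outcome and add it to the Statistical analysis section.
3. Leave the primary infection definition unchanged. Add a sensitivity analysis that excludes events meeting only Criterion 3 and classed as skin reaction. Fix the classification rule in advance and apply it blind to the A/B code, using the recorded antibiotic reason, the absence of pus and dehiscence, and the swab result that is already planned.

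The cost is a few questions per call, one extra table and one extra analysis. There are two downsides. Calls become slightly longer. The sensitivity analysis may also drop some true infections, possibly more in the copper arm, which would favour copper. It should therefore be labelled as supportive and not replace the primary result.

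### Should the plan fix a risk ratio with a 95% interval for each wound type, adjusted for delivery category, instead of saying only that infection rates will be compared?

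*Combined protocol and SAP*

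**What the plan says.** The Statistical analysis section has two sentences on the comparison. The first separates the wound types: "Infection rates in the perineal tear group and the caesarean section group will be analysed". The second is "The infection rates in the study group (with copper) will be compared to the control group and possible risk factors for infection will be explored". The Objectives section gives each wound type its own primary objective, and the Methodology section tells women "about the four arms of this study", so a copper-versus-control comparison within each wound type is clearly meant.

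The Randomisation section states: "After inclusion all patients will be randomised for a wound dressing or maternity pad with (study group) or without copper (control group". It gives no allocation ratio and no stratification. Delivery category is part of eligibility: "Delivered by caesarean section (emergency or elective") for the caesarean group, and "or vaginally, sustaining a perineal tear or episiotomy which needed to be sutured" for the perineal group. The section on patient data says that delivery details are collected. The datasheet is an appendix that is not in the text, so it is a fair inference, not a certainty, that the category is recorded.

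The perineal population is described in two ways. Objective 2 reads "To assess the effect of copper impregnated maternity pads on the incidence of wound infection of second degree perineal tears following vaginal delivery". The hypothesis expects that copper "reduces infection rates in perineal lacerations, episiotomies and caesarean section wounds".

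**The concern.** The two primary objectives are about the effect of copper on infection, so the trial will report an effect even though it is a pilot. With no measure fixed, the same data can look different. For an assumed 30% relative reduction from a 41% control rate, the risk ratio is 0.70, the odds ratio 0.58 and the difference 12.3 points. From a 7% control rate they are 0.70, 0.68 and 2.1 points. The open-ended look at risk factors could also supply an adjusted model chosen after the fact.

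Second, randomisation is not stated to be stratified, and about two thirds of caesareans are emergencies. If emergencies carry more infection, a chance surplus of them in one arm would move the crude result. Adjustment for a variable that is probably on the datasheet looks like a free remedy.

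**Working it through.** The plan states no sample size, power or event count, so there is no figure of its own to reproduce.

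**Inputs from the documents**
- Maternity statistics table: 696 of 1,018 caesareans are emergencies, w = 0.684; 643 of 1,977 sutured perineal wounds are episiotomies, w = 0.325.
- Background: infection in 7% to 41% of caesareans and 11% of sutured tears.

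**Assumptions (not in the documents)**
- 1:1 simple randomisation.
- 50% uptake, giving about 254 caesarean and 494 perineal women per arm over 12 months.
- Risk ratio k between delivery categories of 1.25 to 2.

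**1. Precision gained by adjusting.** With overall rate r, the category rates are lo = r/(1 − w + wk) and hi = k·lo. The share of outcome variance removed is R² = w(1 − w)(hi − lo)²/[r(1 − r)], and the interval narrows by 1 − √(1 − R²).

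| Group | r | k | hi / lo | R² | Narrowing |
|---|---|---|---|---|---|
| Caesarean | 7% | 1.25 | 7.5% / 6.0% | 0.07% | 0.04% |
| Caesarean | 7% | 2 | 8.3% / 4.2% | 0.57% | 0.29% |
| Caesarean | 20% | 2 | 23.8% / 11.9% | 1.9% | 0.96% |
| Caesarean | 41% | 1.25 | 43.8% / 35.0% | 0.69% | 0.34% |
| Caesarean | 41% | 2 | 48.7% / 24.4% | 5.3% | 2.7% |
| Perineal | 11% | 1.25 | 12.7% / 10.2% | 0.14% | 0.07% |
| Perineal | 11% | 2 | 16.6% / 8.3% | 1.5% | 0.8% |

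At an extreme k = 3 the narrowing is 0.6% (7%) to 5.5% (41%) for caesareans and 2.0% for perineal wounds.

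**2. Power.** Simulated with a true 30% relative reduction, 254 per arm and k = 2, crude versus Mantel-Haenszel:
- control rate 7%: 15.0% versus 15.1%
- 11%: 23.5% versus 23.5%
- 20%: 42.7% versus 43.1%
- 41%: 82.5% versus 84.0%

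With 64 per arm and a 7% rate (no true effect), the variance of the adjusted log risk ratio was 0.4% to 0.9% larger, so nothing was gained. In a separate simulation with a true risk ratio of 0.7, the mean crude and adjusted log risk ratios agreed within 0.0005, so the crude estimate is not systematically off.

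**3. Chance imbalance.** The 95% range of the between-arm difference in emergency share is ±1.96·√[2w(1 − w)/n] = ±1.96·√(2 × 0.684 × 0.316/254) = ±8 points. A gap above 10 points has probability 1.5%. An 8-point gap with no copper effect and k = 2 gives a crude risk ratio of (1 + 0.684 + 0.04)/(1 + 0.684 − 0.04) = 1.724/1.644 = 1.05. With k = 1.25 it is 1.181/1.161 = 1.02.

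**4. The interval this sits in.** With no true effect the 95% interval is exp(±1.96·√[2(1 − r)/(nr)]). For n = 254 it is 0.53 to 1.89 at 7% and 0.81 to 1.23 at 41%. A shift of 2% to 5% is small beside either, and the crude interval already allows for chance imbalance of this kind.

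**The case for a change.** The best argument for a change is not precision but commitment. A few sentences, at no cost in women, visits or data, would settle which estimate is the result and would stop a visible imbalance from prompting a late choice of model. An interval also matters in a pilot: two bare rates hide an uncertainty as wide as 0.53 to 1.89, and a larger trial may be planned from them.

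It stands that writing this down is good practice and harmless. It does not stand that the omission misleads. Ratio, odds ratio and difference all come from the same two-by-two table and agree in direction, so a report with counts per arm lets a reader obtain any of them with an interval. The plan mentions the search for risk factors as something beyond the copper comparison, not as its model. Nor would the proposed wording close the remaining choices: infection is asked about at days 7, 14 and 30 with no primary time point named, and that choice would stay open whatever the measure.

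The perineal mismatch also stands as a fact. Read literally, Objective 2 covers 1,334 women a year, not 1,977, a third fewer. At 50% uptake and 11% infection the no-effect interval is then 0.65 to 1.54 (334 per arm) against 0.70 to 1.43 (494 per arm). The inclusion criterion would even admit a sutured first degree tear, which neither Objective 2 nor the table counts. But this is a question of whom the objective covers. A risk ratio or a covariate does not answer it, and under the narrow reading the tear/episiotomy covariate disappears.

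**Conclusion.** No change to the plan follows. The missing effect measure and interval are detail that any competent analysis of two infection rates supplies, and the unadjusted randomised comparison is valid. The only substantive proposal, adjustment for delivery category, has no demonstrated gain. The interval narrows by 0.04% to 2.7% for caesareans and by 0.07% to 0.8% for perineal wounds, and a case-mix gap at its 95% limit moves the caesarean risk ratio by about 2% to 5%.

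These sizes rest on assumed 1:1 allocation, 50% uptake and category risk ratios of 1.25 to 2. Lower uptake would bring the comparison closer to the setting with no gain. A much stronger link between category and infection would raise the gain, but even a threefold risk gives at most 5.5%, and only at a 41% infection rate. An analyst who wishes to show an adjusted estimate beside the crude one can do so if the datasheet records the category; the conclusion should not depend on it.
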